Physical & HP (H&P due day 1, EOT and 30	X	Days 1, within 3 days	X within 3 days of	X within 3 days of dosing day 1	X	X	

day)		D15 (pre-nivo)	dosing day 1				
Vitals ^{1,8}	X	Days 1, within 3 days D15 (pre-nivo)	X within 3 days of dosing day 1 and day 15	X within 3 days of dosing day 1 and day 15	X	X	
Conmeds ¹⁷	X	Days 1, within 3 days D 15 (pre-nivo)	X within 3 days of dosing day 1 within 3 days of dosing day 1 and day 15	X within 3 days of dosing day 1 within 3 days of dosing day 1 and day 15	X	X	
PS	X	Days 1, within 3 days D 15 (pre-nivo)	X within 3 days of dosing day 1	X within 3 days of dosing day 1	X	X	
AE assessment	X	Days 1, within 3 days D 15 (pre-nivo)	X within 3 days of dosing day 1 within 3 days of dosing day 1 and 15	X within 3 days of dosing day 1 within 3 days of dosing day 1 and 15	X	X	
DLT assessment	X	Days 1, within 3 days D 15 (pre-nivo)	X (DLT assessment completed pre-cycle 2 day 1)				
EKG ¹⁶		as clinically indicated	as clinically indicated	as clinically indicated	as clinically indicated		
CT C/A/P ³			At week 8 (+1 week) ³	Every 8 weeks (+1 week) ³	X unless one was completed in prior 4 weeks		X ³
Brain MRI for patients with brain mets 3			X	X	X unless one was complet		X ³

					ed in prior 4 weeks		
Bone scan or bone X-Ray for patients with bone metastases ³		X	X	X unless one was completed in prior 4 weeks		X ³	
CBC w/diff, plts ^{4,8}		⁸ Weekly within 24 hours of dosing each day	X within 3 days of dosing day 1 and day 15	X within 3 days of dosing day 1 and day 15	X		
Serum chemistry ^{5,8}		⁸ Weekly within 24 hours of dosing each day	X within 3 days of dosing day 1 and day 15	X within 3 days of dosing day 1 and day 15	X		
TSH and coagulation ^{6,8}		⁸ X D1 only	X within 3 days day 1 only	X within 3 days day 1 only	X		
HCG ^{7,8}		X ^{7,8}	X	X			
PK plasma ⁹ (Phase IB patients only)	X ⁹	X ⁹ See schedule for all requirements D1,2,3,7	X ⁹ See schedule for all requirements D1,2,3,7	X ⁹			
Blood sample for PD ¹⁰	X ¹⁰	X ¹⁰ See schedule for all requirements D1,2,3,7	X ¹⁰ See schedule for all requirements D1,2,3,7	X ¹⁰			
cfDNA ¹¹		X prior to D15 dosing	X	X			
Tumor biopsy ¹³⁺¹²			Week 8 (+/- 7 days)		Biopsy at progression if patient has not progressed ¹³		

Survival and disease status							X ¹⁵
-----------------------------	--	--	--	--	--	--	-----------------

*ONC201 is to be taken by patient in front of research staff day -7, day 1, day 8, day 15, day 22 in cycle 1.

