Duration of therapy will depend on individual response, evidence of disease progression and tolerance.

In the absence of treatment delays due to adverse event(s), treatment with nivolumab may continue as indicated in each cohort or until one of the following criteria applies:

- Disease progression (see information on patients remaining on study post progression)
- Intercurrent illness that prevents further administration of treatment
- Unacceptable adverse event(s)

- Participant demonstrates non-compliance with treatment regimen and/or required study evaluations
- Participant decides to withdraw from the protocol therapy
- General or specific changes in the participant's condition render the participant unacceptable for further treatment in the judgment of the treating investigator
- Any required toxicity reason as noted in prior sections of the protocol requiring the patient stop treatment
- Any adverse event, laboratory abnormality, or intercurrent illness which, in the judgment of the Investigator, presents a substantial clinical risk to the subject with continued nivolumab dosing
- Oncoceutics decision to forgo further drug development of ONC201

Participants will be removed from the protocol therapy when any of these criteria apply. The reason for removal from protocol therapy, and the date the participant was removed, must be documented in the case report form (CRF). Alternative care options will be discussed with the participant.

10 Efficacy Evaluations

Tumor assessment for solid tumors will include all known or suspected disease sites. Imaging may include chest, abdomen and pelvis CT or MRI scans (when applicable); brain CT or MRI scan for patients with known brain metastases or those with suspected brain metastases; bone scan and/or bone x-rays for patients with bone metastases, if applicable. CT (or MRI) of chest, abdomen and pelvis, will be used for response.

Antitumor activity for patients with solid tumors will be assessed through radiological tumor assessments conducted at baseline, at the end of every other cycle (every 8 weeks), whenever disease progression is suspected (e.g., symptomatic deterioration), and at the time of withdrawal from the study (if not done in the previous 4 weeks).

Assessment of response in these patients will be made using RECIST version 1.1. All patients' files and radiologic images must be available for source verification.

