Duration of stable disease: Stable disease is measured from the start of the treatment until the criteria for progression are met, taking as reference the smallest measurements recorded since the treatment started, including the baseline measurements.

Progression-Free Survival

Overall Survival: Overall Survival (OS) is defined as the time from randomization (or registration) to death due to any cause, or censored at date last known alive.

Progression-Free Survival: Progression-Free Survival (PFS) is defined as the time from randomization (or registration) to the earlier of progression or death due to any cause. Participants alive without disease progression are censored at date of last disease evaluation.

Time to Progression: Time to Progression (TTP) is defined as the time from randomization (or registration) to progression, or censored at date of last disease evaluation for those without progression reported.

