16.3 Efficacy Analysis for Phase II

All patients who have received a minimum of 1 cycle of study treatment, had baseline assessments

and at least one on-study tumor assessment will be considered evaluable for response.

Response rate is defined as the proportion of patients with a Complete (CR) or Partial Response (PR) relative to the total number of evaluable patients. Responses will be defined according to the RECIST version 1.1 guidelines for solid.

The best overall response is the best response recorded from the start of treatment until disease progression/recurrence (taking as reference for progressive disease the smallest measurements recorded since the treatment started) or the withdrawal from the study. Stable disease will be considered the best response when observed at least after two months from baseline. Tumor responses will be analyzed in a descriptive manner. The number and percentage of objective response (CR+PR) will be tabulated. Response rate may be summarized with the corresponding 95% exact confidence interval.

Progression free survival will be defined as the number of days between the first treatment with protocol specified therapy and death or progression, whichever comes first. Individuals who are alive and progression free at last contact will be censored at that time.

Overall survival (OS) will be defined as the number of days between the first treatment with protocol specified therapy and death. Individuals who are alive at last contact will be censored at that time.

Progression free survival and overall survival time distributions in the Phase II study population will be summarized using the methods of Kaplan and Meier.

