16.4 Primary Analysis for Phase II

Following completion of the Phase I trial, we will conduct a single-arm, double endpoint Phase II study to evaluate the efficacy of the promising treatment combination. In Phase II, we will evaluate the co-primary outcomes of response and Progression Free Survival (PFS), testing the composite null hypothesis that P_r , the chance of response, is at most 5% AND the chance of PFS at 3 months, P_s , is at most 50%. The alternative for which power is computed is that the P_r is at least 20% OR P_s is at least 71% (this corresponds to median PFS of 6 months, assuming an exponential model). Our double end-point design (Sill *et al.*, 2012) evaluates an initial cohort of 17 patients. If 1 of 17 respond or 4/17 are Progression Free (PF) at 3 months then recruitment will continue to 34 patients. The null is rejected if there are at least 5/34 responses or at least 22/34 patients PF at 3 mo. Statistics under independence of response and PFS at 3 months (i.e., $P_{rs} = p(\text{response AND PFS at 3 months}) = P_r * P_s$), as well as the most extreme forms of dependence, ($P_{rs} = \min(P_r, P_s)$ or $P_{rs} = \max(0, P_r + P_s - 1)$), were computed. Power: The design provides at least 80% power and at most 7.9% type I error. The chance of early stopping under the null is at least 52% and at most 10.7% under any alternative.

Pharmacokinetic Analysis

All patients who complete at least one day of PK blood sampling will be included in the PK analyses. Plasma concentration/time data of ONC201 obtained at the designated times will be summarized descriptively and presented graphically by dose and day of assessment. The concentration/time data of ONC201 will be analyzed using non-compartmental methods to obtain PK parameters in individual patients. These PK parameters include the maximum plasma

concentration (C_{max}), time to maximum plasma concentration (T_{max}), area under the plasma concentration versus time curve to 24 hours (AUC_{24hr}) and area under the plasma concentration versus time curve to the time of the last measurable concentration (AUC_{last}). If data permit, area under the plasma concentration versus time curve to infinity (AUC_{inf}), terminal elimination half-life ($t_{1/2}$), oral plasma clearance (CL/F) and apparent volume of distribution (Vd/F) will be also estimated.

Individual values and descriptive statistics of these PK parameters will be provided by dose and day of assessment in tabular form.

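### The co-primary count of patients progression free at 3 months rests on two PFS definitions that censor differently, and no rule classifies a patient with no scan at or after month 3

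*Combined protocol and SAP*

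**What the plan says.** PFS is a co-primary endpoint of phase II and is defined twice.

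- **Section 10, under Progression-Free Survival:** "Progression-Free Survival (PFS) is defined as the time from randomization (or registration) to the earlier of progression or death due to any cause". For censoring: "Participants alive without disease progression are censored at date of last disease evaluation".
- **Section 16.3:** "Progression free survival will be defined as the number of days between the first treatment with protocol specified therapy and death or progression". For censoring: "Individuals who are alive and progression free at last contact will be censored at that time".

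Section 16.4 then tests a count out of a fixed 34: "The null is rejected if there are at least 5/34 responses or at least 22/34 patients PF at 3 mo". It refers to neither definition, gives no assessment window for month 3, and has no rule for a patient whose status then is unknown. The evaluability rules in sections 10 and 16.3 concern response only. The replacement rule in section 6.4.3 concerns the phase Ib dose objective.

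On imaging, section 10 asks for "radiological tumor assessments conducted at baseline, at the end of every other cycle (every 8 weeks), whenever disease progression is suspected", and for a scan "at the time of withdrawal from the study (if not done in the previous 4 weeks"). The CT row of the section 8 calendar has the same waiver at the off-study visit: "X unless one was completed in prior 4 weeks". The calendar lists no CT at the 30-day and 100-day safety visits. Footnote 3 requires 8-weekly imaging until progression. It also has a sentence that can be read as leaving restaging after a stable first scan to the investigator's discretion.

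**The concern.** The phase II decision is an exact count with no control arm, so the way one or two patients are classified changes its error rates. A censoring date does not place a patient in a fixed count of 34. Even if section 16.3 is taken to govern because it stands directly before section 16.4, a rule for unknown status still has to be written.

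The two definitions give different answers for the same patient. Take someone with a clean first CT, no later scan, and a contact after month 3. Section 16.3 carries this patient as progression free past month 3. Section 10 censors the same patient at the first CT. If the choice is made once the data are visible, the result can turn on it. Followed as written, section 16.3 pushes the count upward.

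**Working it through.** **Timing.** The first ONC201 dose is on day -7, so cycle 1 day 1 is week 1 from first dose. CT every 8 weeks (+1 week) falls at about weeks 9-10 and 17-18 from first dose, or weeks 8-9 and 16-17 if the interval runs from day -7. Month 3 is about week 13, and no scheduled CT falls there.

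**The plan's own figures.** Inputs from section 16.4: null response 5% and null PF 50%; alternatives 20% and 71%; 17 then 34 patients; final rule 5/34 or 22/34. I enumerated the two-stage bivariate binomial exactly under the three dependence cases that section 16.4 names.

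- With the printed stage-1 rule (1 response or 4 PF), type I error is 8.2-8.6% and early stopping under the null is below 1%. The stated 7.9% and 52% do not reproduce.
- With 2 responses or 10 PF at stage 1, type I error is 7.5-7.9%, early stopping under the null is 51.6-57.1%, minimum power is 79.5%, and early stopping under an alternative is at most 10.7%. This matches the stated figures, so I use it below. The misprint is a separate matter.
- PFS limb alone: P(X ≥ 22 | 34, 0.50) = 6.1%; P(X ≥ 22 | 34, 0.71) = 84.1%.

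**Assumptions, none given in the documents.** PFS is exponential with a 13-week median under the null. An expected m = 1 or 2 of the 34 patients have no scan at or after month 3. They come from those clean at the first CT (week 9 or 10), and missingness is otherwise unrelated to status.

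**Unscanned patients counted as PF, under the null.**

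- S0(t) = 0.5^(t/13), so S0(9) = 0.619 and S0(10) = 0.587.
- The chance q that a patient clean at the first CT is truly PF at month 3 is 0.5/0.619 = 0.81 or 0.5/0.587 = 0.85.
- The observed PF rate is p = 0.5 + (m/34)(1 - q).

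| First CT | m | p | PFS-limb type I error |
|---|---|---|---|
| week 9 | 1 | 0.5057 | 6.9% |
| week 10 | 1 | 0.5044 | 6.7% |
| week 9 | 2 | 0.5113 | 7.8% |
| week 10 | 2 | 0.5087 | 7.4% |

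Putting these p into the two-stage calculation gives overall error of 8.1-8.7% for m = 1 and 8.7-9.6% for m = 2. A first CT at week 8 (S0 = 0.653, q = 0.77, p = 0.5069 or 0.5138) gives slightly more on the PFS limb: 7.1% or 8.3%.

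**Upper figures.** Treat k patients as certain successes who would otherwise each have had a 50% chance: P(X ≥ 22 - k | 34 - k, 0.5) = 8.1% for k = 1 and 10.8% for k = 2. Overall error is 9.2-10.0% and 11.3-12.7%.

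**Unscanned patients counted as not PF, under the 71% alternative.**

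- S1(t) = 0.71^(t/13), so S1(9) = 0.789 and S1(10) = 0.768.
- A patient clean at the first CT is truly PF at month 3 with probability 0.71/S1 = 0.90 or 0.92.
- The observed PF rate is 0.71 - (m/34)(0.71/S1): about 0.683 for m = 1 and 0.656-0.657 for m = 2.
- PFS-limb power falls from 84% to about 74% (m = 1) or 62-63% (m = 2).

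**The case against.** The strongest reply is that few patients will lack a scan, and much of it stands. Sections 8 and 10 call for 8-weekly imaging until progression. Footnote 15 in section 8 collects disease status about every 3 months for 6 months. The note on symptomatic deterioration in section 10 asks for objective progression to be documented even after treatment stops.

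The off-study evaluation is also placed after completion of the whole cycle (footnote 14). A patient who starts cycle 3, at week 9 from first dose, would have it at about weeks 13-14. By then a week-9 CT is 4-5 weeks old, so the waiver is borderline or lost. The gap arises mainly when the first CT was late, or when the patient stops before cycle 3. None of this supplies a counting rule.

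A second reply is that crediting these patients is usually right, because they had a clean first CT. That also stands. It is why 8.1% and 10.8% are upper figures and not the expected size.

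A third is that counting them as failures can cost more power than crediting them costs in error. That is true on the figures above, so the choice should be made openly and in advance.

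A reader might go further and infer that progressions between the first CT and month 3 are missed, so that true type I error is far above 7.9%. The documents do not support a figure. Section 16.4 does not say whether 50% and 71% are true rates or rates seen under 8-weekly CT, and the share of such progressions caught by visits or triggered imaging is unknown.

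**Conclusion.** The concern holds: PFS has two conflicting definitions, and the 22/34 count has no rule for unknown status at month 3. The last-contact rule in section 16.3 biases the count towards declaring activity.

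The likely size is modest. For an expected one or two unscanned patients, crediting them puts overall error roughly 1 to 2 points above the stated 7.9% at most. The opposite rule costs about 10 or 21-22 points of PFS-limb power. These sizes rest on the exponential model, on the assumed number unscanned, and on missingness unrelated to status among patients clean at the first CT. If patients go unscanned because they are deteriorating, crediting them does more harm.

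The start-date conflict needs repair too, but its effect on the count cannot be sized. The documents give a minimum review time before day -7, not the interval from registration to first dose.

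**What to change.** 1. Use one PFS definition in sections 10 and 16.3: from first dose (day -7) to first RECIST 1.1 progression or death, censored at the last disease evaluation and not at last contact.
2. In section 16.4, give month 3 in days from first dose and state that PF status is decided by the first scan at or after that day. Say how progression first seen on that scan is counted, and how a scan taken after new anticancer therapy is treated.
3. Fix, before the data are seen, one rule for patients without such a scan, for both the 17-patient and 34-patient counts. Counting them as not PF is the conservative choice; state its power cost.
4. Report the number unscanned, the count under the opposite rule, and the Kaplan-Meier estimate at 3 months as sensitivity analyses.
5. Reconcile the discretionary sentence in footnote 3 of section 8 with the 8-weekly schedule in the calendar and section 10.

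The changes are to wording and add no scan to the calendar, although they make firm some scans that footnote 3 can be read as leaving open. The stage-1 decision may have to wait for the second CT, about 4-5 weeks after month 3, for patients not yet classified, unless the boundary is already met.

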APPENDIX A Eligibility CHECKLIST

BrUOG 379: Phase Ib/II investigator-initiated, single arm study of ONC201 plus Nivolumab in microsatellite stable (MSS) metastatic colorectal cancer (mCRC) patients

Inclusion criteria:

(y/n) Patients must have a histologically/cytologically-confirmed MSS primary colorectal adenocarcinoma tumor, with confirmation of being microsatellite stable.

(y/n) Radiographic or clinical evidence of metastatic disease that has progressed after at least 2 prior regimens. Prior bevacizumab, cetuximab, trifluridine and tipiracil, or regorafenib is allowed, prior FOLFIRI and FOLFOX treatment is required. (Treatment with a FOLFIRINOX regimen will count as 2 regimens). Prior treatment not required to be have been administered in the metastatic setting.

(y/n) Patients must have measurable disease by RECIST criteria

(y/n) All patients must have a tumor(s) located in an area that can be biopsied as confirmed by treating physician

(y/n) All patients must submit representative tissue from their malignancy if it is confirmed there is enough tissue from prior surgery or most recent biopsy. This can consist of archival tumor samples or tissue collected at biopsy to prove recurrence. In both cases, samples should consist of a formalin-fixed paraffin embedded (FFPE) tumor tissue block or at least 20 unstained slides (charged) of 4 μ M thickness sent to the lab address in section 11.1.4. Tissue located outside of Lifespan Cancer Institute hospitals must be confirmed as requested prior to enrollment.

(y/n) All previous therapies for cancer, including radiotherapy, major surgery and investigational therapies must be discontinued for \geq 14 days before the first dose of ONC201 (D-7 run in).

(y/n) All clinically significant adverse events related to any prior therapy must have resolved to Grade \leq 1 Common Terminology Criteria for Adverse Events (CTCAE v5.0), except alopecia or parameters defined in this eligibility list.

(y/n) Age \geq 18 years.

(y/n) ECOG performance status \leq 2.

(y/n) Adequate organ and marrow function as defined below:

a. Absolute neutrophil count \geq 1,000/mm³ without growth factor use \leq 7 days prior to treatment (this is Day -7) (y/n)

b. Platelets \geq 75,000/mm³ without platelet transfusion \leq 7 days prior to treatment (this is Day -7) (y/n)

c. Hemoglobin \geq 8.0 mg/dL without red blood cell transfusion \leq 7 days prior to treatment (this is Day -7) (y/n)

d. Total serum bilirubin \leq 1.5 X upper limit of normal (ULN) (y/n)

e. AST (SGOT)/ALT (SGPT) \leq 2 X ULN; \leq 5 X ULN if liver dysfunction is felt to be secondary to tumor burden within 14 days prior to treatment (this is Day -7) (y/n)

f. Serum creatinine \leq 1.5 X ULN (OR creatinine clearance \geq 60 mL/min/1.73 m²) within 14 days prior to treatment (this is Day -7) (y/n)

g. Serum or urine pregnancy test (for females of childbearing potential) negative \leq 7 days of treatment (this is Day -7) _____ (y/n)

_____ (y/n) Ability to understand and the willingness to sign a written informed consent document and comply with the study scheduled visits, treatment plans, laboratory tests and other procedures.

_____ (y/n) Female patients of child-bearing potential must be practicing an effective form of contraception from the time of informed consent and for the duration of the study treatment through 5 months after the last dose of drug (ONC201 or Nivolumab, whichever is administered last). The decision of effective contraception will be based on the judgment of the principal investigator or a designated associate.

_____ (y/n) Male patients who are with women of child-bearing potential must be surgically sterile (provide date of surgery) or must agree to use effective contraception from the time of informed consent and for the duration of the study treatment through 7 months after the last dose of drug (ONC201 or Nivolumab, whichever is administered last). The decision of effective contraception will be based on the judgment of the principal investigator or a designated associate.

_____ (y/n) Patients must agree to the required tumor biopsies to enroll in the trial. Pre-treatment biopsies can occur any time post consent and prior to run-in ONC201 dose, a second biopsy will be required at the end of cycle 2 to assess response biomarkers, a final biopsy is included at the time of progression to assess for resistance mechanisms. Only 2 biopsies will be required for patients who initially progress at time of 2nd biopsy.

Exclusion

_____ (y/n) Patients with symptomatic brain metastases are excluded. Patients with asymptomatic and treated CNS metastases may participate in this trial. The patient must have completed any prior treatment for CNS metastases $>$ 28 days prior to registration, including radiotherapy or surgery. Steroids for the treatment of brain metastasis are not permitted.

_____ (y/n) Patients with prior treatment with ONC201 or who have had prior therapy with nivolumab or with an anti-PD-1, anti-PD-L1, anti-PD-L2, anti-CTLA-4 antibody, or any other antibody or drug specifically targeting T-cell co-stimulation or immune check point pathways will be excluded

_____ (y/n) Active inflammatory gastrointestinal disease such as severe chronic diarrhea (unless related to underlying malignancy), gastrointestinal perforation, or intra-abdominal abscess within 6 months prior to study registration. Gastroesophageal reflux disease under controlled treatment with proton pump inhibitors is allowed.

_____ (y/n) Pregnant or breast feeding.

_____ (y/n) Current active treatment in another clinical study (treatment trial) within 14 days of D-7.

_____ (y/n) Uncontrolled intercurrent illness including, but not limited to, ongoing or active infection requiring IV antibiotics, hepatitis, active rheumatologic or collagen vascular disease, symptomatic congestive heart failure, unstable angina pectoris, clinically significant cardiac arrhythmia, or psychiatric illness/social situations that would limit compliance with study requirements.

NOTE: Participants with active or a history of Hepatitis B or C infection as follows:

_____ (y/n) Active hepatitis B (positive hepatitis B surface antigen [HBsAg] or hepatitis C virus (HCV) (positive HCV RNA) are not eligible to participate.

(y/n) HBV carriers or those participants requiring antiviral therapy are not eligible to participate.

(y/n) Participants positive for HCV antibody are eligible only if PCR is negative for HCV RNA. If PCR is positive, they are not eligible to participate.

(y/n) Past HBV infection or resolved HBV infection are may be eligible on this trial provided the following criteria are met prior to randomization: Positive for hepatitis B core antibody (HBcAb), the absence of hepatitis B surface antigen (HBsAg), and no detectable HBV DNA in serum.

(y/n) Known human immunodeficiency virus (HIV) or acquired immunodeficiency syndrome (AIDS)-related illness. (testing is not required for eligibility).

(y/n) Any of the following in the previous 3 months: myocardial infarction, severe/unstable angina, coronary/peripheral artery bypass graft, symptomatic congestive heart failure, cerebrovascular accident, transient ischemic attack or symptomatic pulmonary embolism as defined by treating physician.

(y/n) Other severe acute or chronic medical or psychiatric condition or laboratory abnormality that may increase the risk associated with study participation or study drug administration, or may interfere with the interpretation of study results, or in the judgment of the investigator would make the patient inappropriate for entry into the study.

(y/n) Participants with an active, known or suspected autoimmune disease. Participants with type I diabetes mellitus, hypothyroidism only requiring hormone replacement, skin disorders (such as vitiligo, psoriasis, or alopecia) not requiring systemic treatment, or conditions not expected to recur in the absence of an external trigger are permitted to enroll.

(y/n) Participants with a condition requiring systemic treatment with either corticosteroids (> 10 mg daily prednisone equivalent) or other immunosuppressive medications within 14 days of day 1 of treatment. Inhaled or topical steroids, and adrenal replacement steroid doses > 10 mg daily prednisone equivalent, are permitted in the absence of active autoimmune disease

(y/n) Patients with a history of other invasive malignancies, with the exception of non-melanoma skin cancer are excluded if there is any evidence of other malignancy being present within the last three years (2 years for invasive breast cancer). However, patients with a malignancy that is non-likely to require treatment, as per the treating physician, in the next 2 years, such as a completely resected, early stage breast cancer, or other malignancies treated with curative intent are eligible. Patients are also excluded if their previous cancer treatment contraindicates this protocol therapy.

(y/n) Prior treatment with immunotherapy for any cancer, including immune checkpoint inhibitors or anti-CTLA4 agents

(y/n) Participants who have received a live / attenuated vaccine within 30 days of first treatment.

Signed informed consent: The patient must be aware of the neoplastic nature of his/her disease and must willingly consent after being informed of the procedure to be followed, the experimental nature of the therapy, alternatives, potential benefits, side effects, risks, and discomforts.

The support documentation, per the requirements under the study parameters section of this study, as well as the consent form and this checklist, must be faxed to the BrUOG Central Office at the time of registration. Please check if "Enclosed", state reason when "Not Enclosed," or check if "Not Applicable."

1) Eligibility Form	Enclosed  Not Enclosed  Not Applicable 
2) Heme/Onc initial note	Enclosed  Not Enclosed  Not Applicable 
3) Pathology Report(s)	Enclosed  Not Enclosed  Not Applicable 
4) MRI/CT Report(s)	Enclosed  Not Enclosed  Not Applicable 
5) Lab Source Document	Enclosed  Not Enclosed  Not Applicable 
6) ICF signature page	Enclosed  Not Enclosed  Not Applicable 
7) Other documentation	Enclosed  Not Enclosed  Not Applicable 

It is required that each item from schedule of evaluations be submitted to BrUOG along with confirmation via source to match each inclusion and confirm each exclusion criteria.

Most recent IRB approval date (whether this be the initial, latest amendment or CR): _____

Date of research biopsy pre-treatment: _____

Date of day -7 treatment: _____

Date of treatment day 1: _____

Hospital where patient will be treated with Oncologist: _____

Name of treating physician: _____

Your signature: _____

